# 3.4.2. Bias Adjustment

This study will use commercial pharmacy claims data to assign exposure status and will use state cancer registry data to identify a diagnosis of osteosarcoma. Pharmacy claims data are not captured for research purposes, but for billing. State cancer registries, however, collect data in part for public health purposes including monitoring of cancer trends. An exact matched cohort design will be used to minimize bias and address confounding.

A confounding factor is an independent risk factor for osteosarcoma that is associated with Forteo exposure. There are, however, few established risk factors for osteosarcoma. Age and sex will be balanced between groups by virtue of the matching. Paget's disease of the bone is a potential confounder. It is not recommended that patients with a history of Paget's disease be treated with Forteo, so we would expect some representation of Paget's disease of the bone only in the comparator population. It is important to note that in the US estimates for the prevalence of this rare outcome are less than 4% (Cooper et al. 2006); therefore, it should not result in appreciable confounding. It is also acknowledged that history of radiation may differ between study cohorts; however, claims data are insufficient to capture this information (for example, a 4- to 6-month look-back period or even longer is not sufficient to measure prior radiation therapy). Related cancer outcomes among patients treated with radiation therapy can take as

long as 10 years or more for solid tumors to develop. Leukemia, the cancer with the shortest expected latency postradiation exposure, can take at least 5 to 7 years to develop (Hall 2000). Research is mixed on other risk factors, and we do not expect them to result in appreciable confounding. As stated by Savage and Mirabello in their 2011 published review article Using Epidemiology and Genomics to Understand Osteosarcoma Etiology, "There are a limited number of proven risk factors associated with osteosarcoma. It occurs more frequently after therapeutic radiation for a different cancer, in individuals with certain cancer predisposition syndromes, and in those with Paget's disease of the bone. However, the majority of osteosarcoma cases occur in the absence of these risk factors. Numerous studies of growth and other genetic risk factors have been conducted but strong data on risk for apparently sporadic osteosarcoma are limited."

Since comparators and Forteo-exposed will be matched on geography, there is no reason to believe that either cohort will have a disproportionate probability of aligning to nonparticipating states.

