### 3.3.4. Time Periods

This study will include linkages between commercial pharmacy claims data and state cancer registry data. A linkage is expected to occur late in 2016 or early in 2017 and will include data from 01 January 2005 through December 2 years prior to the linkage year.

An IRR will be estimated assessing osteosarcoma among patients treated with Forteo compared to a general population control group and an osteoporosis-treated control group. Possible differential mortality between the cohorts will be considered in a sensitivity IRR analysis.

The outcome, osteosarcoma, will be identified using 12 identified ICD-O-3 codes in state cancer registry data (See Table 1 in Attachment 1). These codes are currently used for the prospective US Forteo Patient Registry (GHBX [2]).

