# Attachment 1. Adult Patients Treated with Forteo by Age Group, National Drug Codes, and ICD-O-3

# ICD-O-3 CODES

Table 1: Osteosarcoma ICD-O-3 diagnosis codes			
9180/3	Osteosarcoma NOS	9186/3	Central osteosarcoma
9181/3	Chondroblastic osteosarcoma	9187/3	Intraosseous well differentiated Osteosarcoma
9182/3	Fibroblastic osteosarcoma	9192/3	Parosteal osteosarcoma
9183/3	Telangiectatic osteosarcoma	9193/3	Periosteal osteosarcoma
9184/3	Osteosarcoma in Paget's disease of Bone	9194/3	High-grade surface osteosarcoma
9185/3	Small cell osteosarcoma	9195/3	Intracortical osteosarcoma

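### A prevalence below 4% does not show that Paget's disease is a negligible confounder; the bias also depends on its relative risk, which the protocol omits, and it would attenuate an excess risk

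*Protocol*

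**What the plan says.** Section 3.4.2 (Bias Adjustment) of the protocol says that "Paget's disease of the bone is a potential confounder". Because Forteo is not recommended for patients with that history, it continues, "so we would expect some representation of Paget's disease of the bone only in the comparator population". The dismissal comes in the next sentence: "estimates for the prevalence of this rare outcome are less than 4" per cent; "therefore, it should not result in appreciable confounding". No relative risk and no bias calculation accompany it.

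Later the same section quotes a review in which osteosarcoma is said to be more frequent after therapeutic radiation, "in individuals with certain cancer predisposition syndromes, and in those with Paget's disease of the bone". The review adds: "However, the majority of osteosarcoma cases occur in the absence of these risk factors".

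On the outcome, section 3.3.4 says: "The outcome, osteosarcoma, will be identified using 12 identified ICD-O-3 codes in state cancer registry data". Table 1 of Attachment 1 lists the 12 codes; one is 9184/3, "Osteosarcoma in Paget's disease of Bone".

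The matching variables in sections 3.3.3.2 and 3.4 are age group, sex, zip code, payer type, calendar month and a count of therapeutic classes. Paget's history appears only in the optional secondary objective (3.2.2.1), as a baseline factor for comparing the cohorts through medical claims.

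**The concern.** The step from low prevalence to no appreciable confounding is invalid. A rare factor confounds little if it is weak, but can confound noticeably if it is strong. The protocol gives only half of what is needed, while its own quoted source treats Paget's disease as a proven risk factor.

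The direction matters. If the factor is concentrated in comparators, their osteosarcoma rate is raised and the IRR falls. In a safety study that attenuates a true excess risk.

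Nothing in the design removes the imbalance. Paget's disease is not a matching variable, neither comparator definition excludes it, and osteosarcomas coded as arising in Paget's disease count as events in the primary analysis.

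**Working it through.** **Inputs from the protocol**
- Prevalence among comparators, p_C: below 4% (3.4.2). This is an upper limit with no age-specific value.
- Prevalence among Forteo users, p_F: expected to be about 0 (3.4.2). This is an expectation, not an exclusion criterion.
- Share of cases without the listed risk factors: a majority (review quoted in 3.4.2). It covers all the risk factors together and is not specific to age.
- Relative risk of osteosarcoma in Paget's disease, RR: above 1, size not given. Values of 2 to 20 are assumed below.

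The protocol states no bias figure, so there is none to reproduce.

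**Step 1. Bias factor.** For an unmeasured binary confounder,

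IRR observed / IRR true = [1 + p_F(RR − 1)] / [1 + p_C(RR − 1)].

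With p_F = 0 this is 1 / [1 + p_C(RR − 1)]. For example, at p_C = 4% and RR = 10 it is 1 / (1 + 0.04 × 9) = 1/1.36 = 0.735.

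| p_C | RR 2 | RR 5 | RR 10 | RR 20 |
|---|---|---|---|---|
| 0.5% | 0.995 | 0.980 | 0.957 | 0.913 |
| 1% | 0.990 | 0.962 | 0.917 | 0.840 |
| 2% | 0.980 | 0.926 | 0.847 | 0.725 |
| 4% | 0.962 | 0.862 | 0.735 | 0.568 |

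A true IRR of 2 would be seen as 1.98, 1.92, 1.83 or 1.68 across the 1% row, and as 1.92, 1.72, 1.47 or 1.14 across the 4% row.

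**Step 2. What a 20% attenuation requires.** Solving 1 / [1 + p_C(RR − 1)] = 0.8 gives RR = 1 + 0.25/p_C: 7.25 at 4%, 13.5 at 2% and 26 at 1%.

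**Step 3. Some Paget's disease among Forteo users.** With p_F = 1%, p_C = 4% and RR = 10, the factor is (1 + 0.09)/(1 + 0.36) = 1.09/1.36 = 0.80, against 0.74 with p_F = 0. The bias shrinks but remains.

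**Step 4. The limit set by the quoted review.** Let f be the share of comparator cases with Paget's disease, f = p_C·RR / [1 + p_C(RR − 1)]. With p_F = 0 the factor can also be written (1 − f)/(1 − p_C). If most comparator cases lack these risk factors, f is below 0.5 and the factor stays above 0.5/0.96 = 0.52 at p_C = 4%, or 0.5/0.99 = 0.505 at 1%. A true IRR of 2 would then be seen as at least about 1.04 or 1.01. The 4%, RR 20 cell has f = 0.80/1.76 = 45%, just inside the limit.

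**Step 5. What excluding code 9184/3 would do.** If every Paget-related case carried that code, the exclusion would remove all excess comparator cases but leave the person-time of Paget's patients in the denominator. With p_F = 0 the resulting IRR is the true IRR times 1/(1 − p_C), at most 1/0.96 = 1.04.

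**The case against.** The best defence is that the section does not rest on prevalence alone. The quoted review says most cases arise without these risk factors, and that bears directly on how large the bias can be. This stands, and it has a consequence. A reader might take 4% prevalence with a relative risk of 30, obtain 1/2.16 = 0.46, and conclude that a true IRR of 2 would appear as 0.93 and be hidden entirely. That combination makes 1.20/2.16 = 56% of comparator cases Paget-related, which conflicts with the review's statement. Still, the protocol does not connect that statement to the Paget's sentence, and a limit of about one half is far from no appreciable confounding.

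Second, a reader might treat zero prevalence among Forteo users as fact. The protocol only expects it, and step 3 shows a smaller bias otherwise.

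Third, other provisions touch the issue. The optional objective compares Paget's history between cohorts, and section 3.4 says cases will be described and foresees data-driven sensitivity analyses. The first is descriptive and relies on a linkage that section 3.3.2 expects to be very low: an initial estimate of 4% of Forteo users for enrollees with medical and pharmacy coverage, although those with medical coverage only are also eligible. The second depends on case numbers and a qualitative look, and commits to no Paget-specific analysis.

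Fourth, a sensitivity analysis without one histology code commonly belongs in the statistical analysis plan, which is not at hand. Its absence from the protocol is therefore not the fault. The fault is the inference printed in section 3.4.2.

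**Conclusion.** The point holds as a flaw in stated reasoning, with a bias of uncertain size and, on the protocol's own expectation, a known direction. Prevalence below 4% does not establish that confounding is negligible. If Paget's disease is more common among comparators, the IRR is biased downwards.

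The size rests on a relative risk that the protocol does not supply. With none among Forteo users, the factor runs from 0.99 (RR 2) to 0.84 (RR 20) at 1% prevalence and from 0.96 to 0.57 at 4%. It is negligible for a weak risk factor or a prevalence well below 1%. It becomes material, at 20% or more, from a relative risk of about 7 at the protocol's upper limit of 4%.

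The documents support possible attenuation of a true excess. They do not support complete masking of a true IRR of 2, provided that the statement about the majority of cases carries over to this older cohort, which the protocol does not show.

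**What to change.** 1. Replace the sentence that argues from prevalence below 4% with a short table of the bias factor over stated ranges: p_C including values below 1%, p_F including values above 0, and RR including 2 to 5. Note the constraint from the majority-of-cases statement. Section 3.4.1 already sets a precedent by planning assumed differences and a tipping point for differential mortality.
2. Keep the 12-code outcome as primary. Prespecify a sensitivity IRR against each comparator that excludes ICD-O-3 code 9184/3 from the outcome in both cohorts. Any 9184/3 case in a Forteo user should still be described, since it is itself a safety observation.
3. State the limits of that exclusion. Paget-related cases recorded under another code remain, so the correction may be incomplete. Keeping the person-time of Paget's patients can shift the IRR upwards by a factor of at most 1/(1 − p_C), about 4%.

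The cost is one extra model run per comparator and a paragraph of text. Section 3.5.2 already asks the registries for the diagnosis codes, and the primary analysis does not change.

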# 3.4.3. Scope of Inference

The findings from this study should be considered as complementary to others with proper consideration given to various differences in geographic distribution, payer types, comparator population selection, and matching techniques. Currently the IMS database contains data for over 220 million unique de-identified patients and 1 million physicians. Data are consistently robust across all regions of the country, ranging from 57% coverage in the Southwest to 70% to 80% in the Mid-Atlantic region. The LRx represents >85% of all US retail prescriptions and 40% to 75% of US specialty and mail-order prescriptions (depending on therapeutic area). IMS documents the saturation of pharmacies in LRx at the state and the MSA level. These internal IMS data can be used to estimate data completeness. Of note, there is potential overlap with the parallel study (Study GHBX Addendum 2.2) being conducted covering the 65-and-older Medicare population.

Limitations of the pharmacy data include a potential for Forteo drug exposure misclassification:
1) for patients who received Forteo from pharmacies outside of the coverage area or from pharmacies with inconsistent data contributions to LRx (that is, underreporting) and, 2) assuming dispensed Forteo prescriptions were truly administered to patients (that is, over-reporting or overestimation).

# 3.4.4. Subgroups

There are no planned subgroup analyses. The focus of this study is to evaluate patients exposed to Forteo versus comparators unexposed to Forteo.

# 3.4.5. Multiplicity

Multiplicity is not a concern given incidence rates and IRRs will be estimated at planned linkages.

The study described in this protocol and a parallel postauthorization database study are assessing the risk of osteosarcoma independently and are using 2 independent data sources. Given the size

and scale of both data sources it is likely there will be overlap of patients in the commercial claims database and the Medicare database among patients aged 65 and older. This is not a concern as each study will assess their data and interpret the findings independently. After completion of the analysis, the findings from each study will be qualitatively compared for the population aged 65 years and older.

# 3.4.6. Missing Data

Patients with missing information in the pharmacy claims on variables used for matching will be dropped during the cohort selection process, with the possible exception of sex. If matching cannot be achieved for a particular matching variable, that variable will be dropped from the matching process and controlled for in the IRR analysis (if deemed necessary). If fewer than 5% of the Forteo-exposed cohort are described as having an unknown sex, these patients will be dropped prior to matching to limit bias introduced from potentially mismatching patients on a risk factor (males have higher incidence and females may develop osteosarcoma at younger ages than do males [ACS 2014]). If ≥5% of Forteo-exposed has an unknown sex, these patients will be retained and matched to comparators with an unknown sex.

Patients will be eliminated or reported as unknown from any descriptive reporting where required data fields are missing, but will remain in the primary analysis. The Forteo-exposed cohort with missing or invalid days' supply and quantity dispensed values on 1 or more Forteo-dispensed prescription claims between index and the earlier of end of study period or date on which osteosarcoma is detected will not be included in assessment of cumulative Forteo exposure.

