### 3. Observational Research Protocol

### 3.1. Rationale

Forteo (teriparatide) was initially approved in 2002 in the United States (US) for the treatment of postmenopausal women with osteoporosis at high risk for bone fractures and for increasing bone mass in men with primary or hypogonadal osteoporosis who are at high risk for fracture. In 2009, the treatment indication was expanded to include treatment of men and women with glucocorticoid-induced osteoporosis who are at high risk for fracture.

In rats, in one 2-year (near-lifetime) toxicology study in which doses were administered at levels that produced systemic exposures 3 to 60 times greater than that of a 20- $\mu$ g dose in humans, teriparatide caused increases in bone mass and a dose-dependent increase in the incidence of osteosarcoma, a malignant tumor (Vahle et al. 2002; Forteo USPI 2012). A subsequent rat study conducted to determine the effect of duration of treatment and age at initiation of treatment found that the bone neoplastic response in rats was dependent on both dose and duration of treatment. The study established a "no-effect" dose of 5  $\mu$ g/kg when initiated at 6 months of age, and continued for a duration of either 6 months or 20 months (Vahle et al. 2004). In a long-term study of cynomolgus monkeys (spanning 18 months of treatment plus 3 years of follow-up observation), no bone tumors were detected by radiographic or histological evaluation (Vahle et al. 2008). Studies have shown that the rat skeleton is more sensitive than monkey or human skeletons to the pharmacological effects of parathyroid hormone in the formation of new bone and osteosarcomas (Miller 2008).

Osteosarcoma has rarely been reported in people who have received treatment with Forteo. It is not known if patients who are treated with Forteo have a higher risk of osteosarcoma; however, there have been spontaneous reports of osteosarcoma in Forteo-treated patients.

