# 3.2.2. Secondary Objective(s)

To characterize the Forteo user and comparator cohort using the following:

- Demographic characteristics
- Select prescription drugs dispensed during the baseline period
- Duration of Forteo use for Forteo-treated cohort
- Provider specialty

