### 3.3.2. Data Sources

### IMS Longitudinal Prescription (LRx) Data

The IMS Health (IMS) longitudinal prescription database (LRx) consists of patient-level dispensed prescriptions that enable patient prescription-filling behavior to be tracked across time, payers, and pharmacies. Data contributors include retail chains and independent pharmacies, specialty, mail-order, and long-term care pharmacies. The LRx captures prescriptions purchased through all methods of payment (for example, cash, Medicaid, third party). Currently, the database contains data for over 220 million unique de-identified patients and 1 million physicians. Data are consistently robust across all regions of the country, ranging from 57% coverage in the Southwest to 70% to 80% in the Mid-Atlantic region. The LRx represents >85% of all US retail prescriptions and 40% to 75% of US specialty and mail-order prescriptions (depending on therapeutic area). The IMS documents the saturation of pharmacies in LRx at the state and the Metropolitan Statistical Area (MSA) level; these internal IMS data can be used to estimate data completeness. The LRx data are available from 2005.

The database includes de-identified patient-level longitudinal data such as age, sex, zip codes, dispensed drug (through National Drug Code [NDC]), molecule, form, strength, quantity, and days' supply. All data are Health Insurance Portability and Accountability Act (HIPAA) compliant to protect patient privacy.

There are limitations to using pharmacy claims data for research purposes. Claims data are generated primarily for reimbursement purposes and not research. One such limitation is potential misclassification given that exposure is identified based on a claim for a dispensed prescription without information that confirms whether or not the patient actually used the medication. Based on market research data, 70% of new patients refill their Forteo prescription at least once, and 64% refill their prescription to cover at least 90 days. Therefore, the potential for exposure misclassification is likely to be minimal. In addition, LRx is an open source claims database with data contributed by pharmacies, not health plans. As such, the completeness of data capture is contingent upon the consistency of data contributions from pharmacies.

The patient counts for Forteo from LRx are as follows:

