Descriptive characteristics will be reported for both the Forteo-exposed and comparator cohorts (See Table 1). Among the Forteo cohort, drug utilization patterns will be reported including the number of dispensed prescriptions, mean days of supply, dosage form and strength. Baseline characteristics will be reported in total and stratified by reporting age categories. The number and percent of patients along with descriptive statistics (mean, standard deviation, median, 25th and 75th percentiles) will be reported for continuous data. Categorical variables (for example, payer type) will report the number and percent of patients. Baseline characteristics reported in Table 1 will be summarized for both cohorts.

Two time periods are included with variable look-back windows for assessment of osteosarcoma diagnosis postcohort entry using a data-driven approach. Additionally, 2 comparator cohorts will be established and analyzed. The analysis will be conducted using the following scenarios:

- Primary time period: Using the full 10 years of data available for Forteo exposure and the matched cohort. This will be January 2005 through December 2 years prior to the linkage. State cancer registry data will be linked to all data during this window. This approach assesses all available data and provides a more comprehensive analysis.
- Secondary time period: Using a data-driven approach, a sensitivity analysis will be conducted. This sensitivity analysis will include a variable look-back window where the exposed cohort will only be included when at least a 3-month look-back period is available prior to the index date to describe baseline characteristics.

Findings from these analyses will be described and compared.

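### One unusable Forteo claim removes the whole patient from the cumulative-exposure summary, so longer users are lost more often and that descriptive summary is biased low

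*Protocol*

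**What the plan says.** Section 3.4.6 of the protocol sets the rule. The trigger is "missing or invalid days' supply and quantity dispensed values on 1 or more Forteo-dispensed prescription claims", checked "between index and the earlier of end of study period or date on which osteosarcoma is detected". The consequence falls on the patient: the patient "will not be included in assessment of cumulative Forteo exposure". No claim-level handling and no sensitivity analysis is given for this rule.

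The sentence just before it limits the reach of missing descriptive fields: "Patients will be eliminated or reported as unknown from any descriptive reporting where required data fields are missing, but will remain in the primary analysis".

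Three other places bear on the point:
- Section 3.2.2 lists, among the characteristics to be described as a secondary objective, "Duration of Forteo use for Forteo-treated cohort".
- Section 3.4.1 says that for the Forteo cohort "drug utilization patterns will be reported including the number of dispensed prescriptions, mean days of supply, dosage form and strength".
- Section 3.1 gives the reason for interest in duration: in the second rat study, "the bone neoplastic response in rats was dependent on both dose and duration of treatment".

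**The concern.** The exclusion depends on something close to the quantity being summarised. A patient with one fill has one chance of an unusable record. A patient with two years of monthly fills has 24. A rule that drops the patient at the first bad record therefore removes long users more often than short ones, and those who remain have, on average, less exposure than the cohort. A large cohort does not cure this, because it is a selection effect and not sampling noise.

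What is at stake is descriptive. The exposure summary tells the reader how much long-term use lies behind the incidence rate ratio. Given the rat findings, a reader will look there first for reassurance that long use was well represented, and the rule would understate it.

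**Working it through.** The protocol states no per-claim error rate, no expected share excluded and no other figure on this point, so there is nothing to reproduce. The mechanism can be checked over a range.

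**Inputs.** From section 3.4.6: one unusable claim is enough, and the whole patient is excluded. From section 3.3.2: "70% of new patients refill their Forteo prescription at least once, and 64% refill their prescription to cover at least 90 days". Assumed, because the protocol does not give them: the per-claim rate q, monthly fills, and the spread of claims among longer users.

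**Step 1. Exclusion by number of claims n, independent errors.** P(excluded) = 1 − (1 − q)^n. For example, at q = 1% and n = 24: 1 − 0.99^24 = 21.4%.

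| q | n = 1 | n = 3 | n = 12 | n = 24 |
|---|---|---|---|---|
| 0.1% | 0.1% | 0.3% | 1.2% | 2.4% |
| 0.5% | 0.5% | 1.5% | 5.8% | 11.3% |
| 1% | 1.0% | 3.0% | 11.4% | 21.4% |
| 2% | 2.0% | 5.9% | 21.5% | 38.4% |

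**Step 2. Effect on an average, illustration only.** Take 30% of patients with one claim (100 − 70), 6% with two (70 − 64), and the other 64% spread evenly over 3 to 24 claims. The mean is 0.30 × 1 + 0.06 × 2 + 0.64 × 13.5 = 9.06 claims. If every claim covers the same number of days, mean claims among retained patients stands in for mean cumulative exposure. Weighting each n by (1 − q)^n gives:

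| q | patients dropped | mean claims, retained | change |
|---|---|---|---|
| 0.1% | 0.9% | 9.00 | −0.7% |
| 0.5% | 4.4% | 8.76 | −3.3% |
| 1% | 8.4% | 8.46 | −6.6% |
| 2% | 15.7% | 7.88 | −13.0% |

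At q = 1% the dropped patients average 15.6 claims.

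**Step 3. Errors clustered within patient.** With a beta-binomial model, P(excluded) = 1 − B(a, b + n)/B(a, b), where a = q(1 − ρ)/ρ and b = (1 − q)(1 − ρ)/ρ. At q = 1%, exclusion at 1 claim is 1.0% whatever ρ is. At 24 claims it is 11.4% (ρ = 0.1), 3.7% (ρ = 0.5) or 1.4% (ρ = 0.9), against 21.4% under independence. The direction holds, but the gradient flattens.

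**Step 4. 'And' or 'or'.** Suppose each of the two fields fails independently on 1% of claims. If both must fail on the same claim, the claim-level rate is 0.01 × 0.01 = 0.01%, and exclusion at 24 claims is 0.24%. If either failure is enough, the rate is 1 − 0.99² = 1.99%, and exclusion at 24 claims is 38.3%. The two readings differ by more than a hundredfold in this example. Field failures may well be correlated, which would bring the readings closer together.

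**The case against.** The strongest reply is that the rule touches little that matters. Patients with missing descriptive fields stay in the primary analysis. The incidence rate ratio in section 3.4.1 compares exposed with unexposed person-time and does not use duration. Section 3.4.4 plans no subgroup analyses, and no exposure-response model appears. All of this stands. A reader might infer that the rule weakens the study's test for a duration-dependent hazard, but the protocol plans no such test.

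A reader might also infer that the duration objective in section 3.2.2 is certainly biased. The protocol does not say that duration is computed from days' supply and quantity. Fill dates are captured separately (section 3.3.5, Table 1), and duration could be taken from them. The bias reaches that objective only if it is built from the affected fields. Likewise, counting dispensed prescriptions needs neither field, so the rule does not restrict that output. The undertaking in section 3.4 to describe linked cases is not restricted either, so the documents do not support the reading that a long-use case would drop out of the case description.

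On size, the objection is also largely right. The error rate is unknown, the bias is negligible near 0.1%, and clustering is plausible because section 3.3.2 makes completeness depend on how consistently pharmacies contribute. The literal 'and' may make the trigger rare. The refill figures describe new patients, whereas section 3.3.3.1 admits prevalent users too.

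One part does not stand: that this is detail for the analysis plan. The protocol itself fixes the patient-level exclusion, and it is the rule as written that creates the selection.

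**Conclusion.** The point holds as a directional bias in a secondary, descriptive output. For any per-claim error rate above zero, and unless errors are wholly patient-level, the rule removes longer users more often and pulls the cumulative-exposure summary downward. Its size cannot be fixed from the protocol. In the illustrative cohort with independent errors, the shift in the mean runs from −0.7% at q = 0.1% to −13.0% at q = 2%. It is less with clustering, and much less if both fields must fail and do so independently. These figures rest on the assumed q, monthly fills, equal days per claim and the assumed spread of claims.

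It gives no reason to doubt the primary result. Low severity; a cheap improvement.

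**What to change.** In section 3.4.6, apply the rule to the claim and keep the patient:

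1. State whether a claim counts as unusable when both fields fail or when either one does.
2. If one of days' supply or quantity is valid, derive the other from it.
3. If both are unusable, use the median of the patient's other valid Forteo claims or, if there are none, the modal value for that drug code. Attachment 1 lists only two Forteo codes, so this is simple to specify.
4. Report the share of claims imputed.
5. Show the present complete-case rule as a sensitivity check.

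It would also help to say whether duration of use in section 3.2.2 is derived from these fields or from fill dates.

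The cost is one rewritten data-handling rule and one extra line of reporting. The downside is minor imputation error in a descriptive variable. The primary analysis does not change.
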